7.3.5.1 Sample Collections

Instructions regarding the collection, processing, and shipment of laboratory samples are detailed in a separate laboratory manual. All samples will be given a unique identifier. The sample collection date and time will be entered into the eCRF. Participant age and year of birth will be collected at the time of sample collection and reported on the requisition form.

7.3.6 Assessment of Tolerability During Placebo Run-in and Lixivaptan Titration Period

In the pre-randomization phase of the study, tolerability will be assessed at the end of the Placebo Run-in Period (Visit 3), to maintain participant blinding and at each visit during the Lixivaptan Titration Period (Visits 4 to 9). A single tolerability question will be asked: “Would you take the study drug for the next 24 months?” If the participant confirms the dose can be tolerated, the participant will be titrated to the next dose level (i.e., the dose will be increased). This assessment of tolerability will continue at weekly intervals until either the maximum dose level is reached (Level 4 [200 mg BID]) or until the participant confirms the dose cannot be tolerated for a 24-month period. In that case, the dose will be reduced by one dose level as described in the [Lixivaptan Titration Period \(Part 1\) — Lixivaptan Titration Flowchart](#).

7.3.7 Assessment of Liver Symptoms, Signs, or Test Abnormalities

Testing for hepatic aminotransferases (ALT/AST), alkaline phosphatase, and total bilirubin will be performed at the timepoints as specified in the [Schedule of Procedures – Part 1](#) and [Schedule of Procedures – Part 2](#). Management of hepatic and liver chemistry test abnormalities are discussed below. *The appearance of any suspicious symptoms or signs of liver dysfunction as described in Appendix 2 (Section 13.2) in a participant at any time during the study should trigger prompt testing of liver chemistry tests (i.e., within 48 hours).*

7.3.7.1 Management of Liver Chemistry Test Abnormalities and Signs or Symptoms of Liver Dysfunction Occurring During Study Treatment

Elevations of liver aminotransferase levels >3 x ULN or total bilirubin levels >2 x ULN should prompt immediate retesting within 48 hours. Although central laboratory testing is preferred, local laboratory testing is acceptable, ideally with a concurrent central laboratory sample for confirmation. After the Investigator consults with the medical monitor and sponsor, temporary reduction in dose or interruption of study drug administration must be instituted if liver aminotransferase levels >3 x ULN or total bilirubin levels >2 x ULN are observed during the Lixivaptan Titration or Double-Blind Randomized Treatment Periods of Part 1 or the Lixivaptan Re-Titration or Maintenance Treatment Periods of Part 2. During the time that values remain elevated, testing should be done at least weekly for the first month, gradually returning to monthly as indicated by the results. In the presence of such liver chemistry test abnormalities, additional clinical testing (examples listed in Appendix 3 ([Section 13.3](#))) may be recommended by the medical monitor and sponsor and those results reported according to local guidelines.

Similarly, the appearance of any suspicious symptom or sign of liver dysfunction (see Appendix 2 ([Section 13.2](#))) at any time during the study should trigger prompt testing of liver chemistry (i.e., within 48 hours) and consultation with the medical monitor and sponsor to discuss any changes to dosing with study drug.

All elevations meeting these thresholds or confirmed symptoms or signs of liver dysfunction will be assessed for causality by an independent, blinded Hepatic Events Review Committee (HERC) (see [Section 7.3.7.2](#)).

In the case of study drug interruption, re-starting study drug should be encouraged (see [except under these circumstances](#) below) after discussion with the medical monitor and sponsor, when liver chemistry tests have normalized or stabilized, and in conjunction with a plan for increased frequency of liver chemistry test monitoring.

Treatment with study drug cannot be resumed in participants when:

- aminotransferase levels $>8 \times$ ULN at any time,
- aminotransferase levels $>5 \times$ ULN for more than 2 weeks, or
- concurrent elevations of aminotransferase levels $>3 \times$ ULN and total bilirubin $>2 \times$ ULN

except under these circumstances:

Participants with these levels of abnormality may be re-challenged with study drug if abnormalities were adjudicated by the HERC as having a $\leq 50\%$ likelihood of being related to study drug (per DILI Network [DILIN] probability criteria, modified, Appendix 4 ([Section 13.4](#)) ([Fontana et al, 2009](#)) and the Investigator, medical monitor, and sponsor agree to an intensive monitoring plan to mitigate risk. The participant must also be willing to comply with these monitoring measures, be informed of the potential risks, and agree to study drug re-challenge.

Liver chemistry test increases of a lesser extent (serum aminotransferase levels $\leq 3 \times$ ULN or total bilirubin $\leq 2 \times$ ULN) will be discussed with the medical monitor. They may be related to the underlying variability of such test results in ADPKD patients ([Watkins et al, 2015](#)). Generally, dosing should continue during such lesser liver chemistry test increases; however, the frequency of laboratory testing should increase, particularly during the Double-Blind Randomized Treatment Period in Part 1 and the Maintenance Treatment Period in Part 2. Slowing of titration may also be considered if the abnormalities occur during the Lixivaptan Titration Period in Part 1 or Lixivaptan Re-Titration Period in Part 2.

For participants exhibiting an increase during the Lixivaptan Titration or Lixivaptan Re-titration Periods, follow the instructions in [Section 7.3.7.1.2 \(Liver Test Abnormalities during the Placebo Run-in and/or Lixivaptan Titration Period\)](#).

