4.2.3 Treatment Interruption

In a study of this duration, it is expected that some participants may have one or more treatment interruptions during the Double-blind, Randomized Treatment Period of Part 1 or the Lixivaptan Re-Titration or Maintenance Treatment Periods of Part 2. If a participant’s study drug must be interrupted for medical or surgical reasons, liver chemistry test abnormalities, tolerability issues, temporary use of a prohibited concomitant medication, life situations, e.g., airplane travel, etc... or other reasons, the interruption should be recorded as a “Treatment Interruption” on the eCRF. The participant’s study drug should be resumed as early as the situation allows, e.g., airplane travel ends or recovery from surgery allows re-initiation/re-establishment of study drug treatment. The maximum duration of an interruption is 8 weeks; if interruption is greater than 8 weeks, study drug will be permanently discontinued.

The participant should be instructed to immediately inform the Investigator of any missed doses reaching or expected to reach 2 days or more so that the Investigator can continue to monitor the participant’s treatment and prepare for a possible extended study drug

interruption. The Investigator and/or site staff will notify the CRA and/or medical monitor of a potential interruption within 24 hours.

If a study drug interruption is expected to last 7 or more consecutive days, the participant will be scheduled to have 3 separate serum creatinine and serum cystatin C samples obtained (minimally 24 hrs. apart) beginning on Day 8 after the last dose of study drug for determination of eGFR in the event the study drug interruption leads to permanent discontinuation of treatment. In such cases, the 3rd sample will be collected up to Day 28 (\pm 3 days) after the last dose of study drug. If, in the Investigator's opinion, the treatment interruption is expected to be prolonged (i.e., >4 weeks in duration) or permanent, then a postbaseline MRI will also be obtained.

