4.2.5 Reasons for Treatment/Study Discontinuation

Participants who permanently discontinue study treatment before the end of the study, should be encouraged to continue in the study through the last study visit. They may discontinue or may be discontinued from study drug or from the study for any of the following reasons.

Note: Participants who discontinue from the study following randomization are not eligible to re-enroll.

1. Noncompliance with the protocol (protocol deviation);
2. Noncompliance with study drug;
3. Lack of efficacy (including need for transplantation or dialysis);
4. A serious or intolerable AE that, in the Investigator's opinion, requires discontinuation of study drug or permanent withdrawal from the study, including but not limited to laboratory safety assessments that reveal clinically significant (CS) hematological or biochemical changes from the baseline values, other than changes that are expected for vasopressin antagonists, and symptoms or an intercurrent illness that justifies withdrawal. Mild elevations in serum creatinine or serum sodium are known pharmacodynamic effects of vasopressin antagonists like lixivaptan and are transient and reversible. Therefore, participants should not be withdrawn due to mildly elevated serum creatinine or serum sodium and should be discussed with the medical monitor, if necessary;
5. Death;
6. Lost to follow-up (detailed procedures to prevent such loss are discussed further);
7. Withdrawal of consent (partial or complete);
8. Investigator or sponsor decides to discontinue the participant's participation in the study;
9. Pregnancy;
10. Site terminated by sponsor;
11. Study terminated by sponsor;
12. Other (e.g., trial burden, development of contraindication to use of study drug).

Upon occurrence of an SAE or intolerable AE, the Investigator will confer with the medical monitor and sponsor. If a participant is discontinued from study drug because of an AE, the event will be followed until it is resolved or stable as determined by the Investigator.

Additionally, the procedures described in [Section 4.2.4](#) (Treatment Discontinuation) should be followed. Any participant may withdraw his or her consent at any time. Participants' safety will be closely monitored throughout the study, and the study will be conducted following Good Clinical Practices (GCP).

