 - If the participant reports the study drug was tolerated, proceed with titration to the next dose level (via IRT) based on the [Lixivaptan Titration Period \(Part 1\) — Lixivaptan Titration Flowchart](#) and these general principles (**Note:** all study drug assignments will continue to be managed by the IRT system):
 - Level 1 is an introductory dose to allow participants to become accustomed to the aquaretic effects of the study drug.

- The goal of titration is to continue to escalate the dose to achieve either the maximum dose (Level 4 [200 mg BID]) or the highest tolerated dose.
 - In those participants who are titrated up to Levels 3 and 4 but have limited aquaretic tolerability at these dose levels, the reduced dose Levels 3a and 4a are available, respectively, which lower the evening dose by 50 mg. Further dose reductions are allowable as shown in the [Lixivaptan Titration Period \(Part 1\) — Lixivaptan Titration Flowchart](#). This is meant to assist with aquaretic tolerability, and, in particular, nocturia.
 - As shown in the flowchart, most dose levels incorporate a second week of dosing at the same level to assure tolerability. However, as the Lixivaptan Titration Period is designed to be a maximum of 6 weeks in duration, participants will stay on the final tolerable dose for only 1 week if a dose adjustment (i.e., dose decrease) is required at Week 6 (Visit 9/Last Titration). Those participants will immediately proceed to the Double-Blind, Randomized Treatment Period on the newly decreased dose.
- At Visit 4, document CKD Stage based on mean eGFR calculated from Visits 1a, 2, and 3 or Visits 1b, 2, and 3 (if Visit 1b was required).
 - CKD Stage 2: eGFR 60 to 90 ml/min/1.73 m²
 - CKD Stage 3: eGFR 30 to 59 ml/min/1.73 m²
 - CKD Stage 4: eGFR 15 to 29 ml/min/1.73 m²
 - Administer the following health-outcomes scale to participant (**Note:** responses should be reviewed prior to completion of the visit in order to clarify any ambiguous or missing responses):
 - ADPKD-UIS
 - Collect blood samples for the following laboratory testing:
 - Liver chemistry and serum sodium (Visits 5 and 7 only) (**Note:** For participants exhibiting an increase in liver chemistry tests during the Lixivaptan Titration Period (>1.2 x ULN), follow the instructions in [Section 7.3.7.1.2 \(Liver Test Abnormalities during the Placebo Run-in and/or Lixivaptan Titration Period\)](#)).

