7.3.7.1.2 Liver Test Abnormalities during the Placebo Run-in and/or Lixivaptan Titration Period

Serum aminotransferase or total bilirubin levels that are $\geq 1.2 \times \text{ULN}$ to $2 \times \text{ULN}$ during the Placebo Run-in and/or Lixivaptan Titration Period will require holding the dose constant and a discussion with the medical monitor. Levels exceeding $2 \times \text{ULN}$ during the Placebo Run-in and/or Lixivaptan Titration Period will require reducing the dose or discontinuation of study drug (randomization will not occur) depending on the extent of the elevation and in consultation with the medical monitor. Weekly monitoring of liver chemistry tests will be conducted until the values are below the ULN. In consultation with the medical monitor and sponsor, continuation of titration can resume if study drug was continued. If study drug had been stopped, titration can be re-initiated at Level 1 (50 mg BID) with weekly monitoring of liver chemistry tests if the participant agrees to the increased monitoring, is informed of the potential risks, and agrees to re-initiating study drug.

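### Protocol 7.3.7.1 words its three severe liver limits as a bar on restarting drug, not a requirement to stop it, and 7.3.7.1.2 does not mention them

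*Protocol*

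**What the plan says.** **General rule (Protocol 7.3.7.1).** The instruction is that "temporary reduction in dose or interruption of study drug administration must be instituted if liver aminotransferase levels >3 x ULN". It applies equally when total bilirubin exceeds 2x ULN, and it comes after the Investigator has spoken with the medical monitor and sponsor. The rule covers titration, double-blind treatment, re-titration and maintenance. It gives no size for the reduction and no upper level.

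**Severe limits (same section).** A paragraph about restarting after an interruption is followed by: "Treatment with study drug cannot be resumed in participants when" any of these is met:
- aminotransferase >8x ULN at any time;
- aminotransferase >5x ULN lasting more than 2 weeks;
- aminotransferase >3x ULN together with bilirubin >2x ULN.

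The exception is that such participants "may be re-challenged with study drug if abnormalities were adjudicated by the HERC as having a" likelihood of 50% or less of being drug-related. The Investigator, medical monitor and sponsor must also agree an intensive monitoring plan, and the participant must accept the risks.

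**Titration and re-titration.** Section 6.3.1 refers rises in titration to Section 7.3.7.1.2, with the words: "For participants exhibiting an increase in liver chemistry tests during the Lixivaptan Titration Period (>1.2 x ULN), follow the instructions in" that section. It sets no upper level for that referral. Section 7.3.7.1 ends with a similar pointer: "For participants exhibiting an increase during the Lixivaptan Titration or Lixivaptan Re-titration Periods, follow the instructions in" the same place. For values above 2x ULN, Section 7.3.7.1.2 calls for a lower dose or discontinuation, according to how large the rise is. It then says that "continuation of titration can resume if study drug was continued", and that a participant who had stopped may begin again at Level 1 with weekly tests. It does not repeat the three limits or the HERC condition.

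**The concern.** At these three levels the protocol itself wants an independent causality judgement before drug is given again. As worded, that judgement controls dosing only if the first response was to stop. If the first response was to reduce, the participant is still on drug, so nothing is being resumed and the bar has nothing to act on. The third limit is also the combination that SAP Section 9.3.1 tabulates as Hy's Law when the aminotransferase is ALT.

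What is at stake is participant protection in a trial where liver safety is central. Protocol Section 1.9 says no drug-induced liver injury has been reported with lixivaptan so far, but accepts that the risk exists and calls determining it one of two primary objectives. Section 1.4 notes liver failure needing transplantation with tolvaptan, a drug of the same class.

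**Working it through.** The check is textual. The plan states no figure to reproduce.

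1. **What satisfies the rule above 3x ULN?** Reduction or interruption. Either one complies, at 3.1x or at 10x ULN alike.

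2. **What triggers the severe limits?** Their verb is *resumed*, and the HERC exception speaks of *re-challenge*. Both describe giving drug after a gap. Two participants at >8x ULN, both after consultation, compare as follows:

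| First response | Complies with the general rule? | Bound by the three limits? | HERC score of 50% or less needed for further drug? |
|---|---|---|---|
| Interrupt | Yes | Yes | Yes |
| Reduce dose | Yes | Not on the wording | Not on the wording |

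3. **Does HERC review close the gap?** HERC assesses causality for every elevation over the thresholds, whether drug is reduced or stopped. The only dosing consequence stated for an unfavourable score is the bar on re-challenge. No stop is stated for someone still taking a reduced dose.

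4. **Is there a compulsory stopping level elsewhere?**
 - Section 4.2.3 lists cases where drug "must be interrupted for medical or surgical reasons, liver chemistry test abnormalities, tolerability issues" and so on. It says what to do once interruption is needed, not when liver values make it necessary.
 - Section 4.2.5 covers an adverse event that, in the Investigator's opinion, "requires discontinuation of study drug or permanent withdrawal from the study, including but not limited to laboratory safety assessments" results. It gives no liver threshold.
 - Section 5.2 confines dose reduction at the Investigator's own discretion in the double-blind period to non-hepatic effects. That supports the need for consultation, but does not withdraw the hepatic reduction option in 7.3.7.1.
 - Protocol Appendices 2 to 5 and SAP Sections 3.6, 7.2, 9.3.1 and 11.2 contain no such level.

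5. **Titration.** Section 7.3.7.1.2 allows two routes to further drug, continuing or restarting at Level 1, and states neither the limits nor the HERC condition. Section 7.3.7.1 names titration and re-titration in its general rule, and its bar on resuming is not limited by period. For a participant stopped at >8x ULN in titration, one section allows a restart with monitoring and consent, while the other forbids it without the HERC finding. Re-titration is sent to 7.3.7.1.2 although that section's title and text do not mention it.

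6. **Size of a reduction (illustrative only).** Full-level steps in daily dose are 400 to 300 mg (300/400 = 75% remaining), 300 to 200 mg (200/300 = 66.7%) and 200 to 100 mg (100/200 = 50%). Levels 4a and 3a would leave more (350/400 = 87.5%; 250/300 = 83.3%), but Section 5.2 provides them for aquaretic intolerance. With twice-daily dosing, about 2 x 2 = 4 doses fall before the required 48-hour retest. Testing is then at least weekly, so at most 7 x 2 = 14 doses fall between later tests in the first month. Section 7.3.7.1 does not say which step applies to a hepatic event, so none of these percentages measures the problem.

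**The case against.** The best reply is that 7.3.7.1 is a ladder: dosing generally continues up to 3x ULN, is reduced or interrupted above it, and is barred at the three limits unless HERC clears it. Language about resuming and re-challenging presupposes that drug is already off at those levels, and the exception is addressed to participants with those abnormalities. Reduction is only temporary and follows consultation. Continued dosing at >8x ULN would need the Investigator to persist, after consulting the medical monitor and sponsor, at a level where their own protocol forbids resumption. This is persuasive about intent, and the authors probably did mean stopping levels. It does not supply the missing instruction.

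On titration, the reply is that 7.3.7.1.2 sits inside 7.3.7.1, so the limits already apply, and that the closing pointer follows a paragraph on lesser increases. That defeats any claim that titration participants are expressly exempt, which a reader might otherwise infer. It does not remove the conflict, because 6.3.1 refers increases to 7.3.7.1.2 with no upper level and that section permits a restart on its own terms.

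The safeguards are real: retesting within 48 hours, at least weekly tests in the first month while values stay high, HERC review, 24-hour reporting as an event of special interest (7.3.7.2), and an IDMC with unblinded data that receives HERC results and can meet ad hoc (7.3.10). Section 7.3.7.1.2 adds weekly tests until values fall below the ULN. The Investigator or sponsor may also discontinue a participant (4.2.5). These limit the risk. None turns the three limits into a stopping rule.

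**Conclusion.** The gap is real but narrow, and worth fixing. It affects only participants who reach one of the three limits and are dose-reduced rather than stopped, or who are continued or restarted in titration or re-titration. The documents give no rate for this, so no case count or probability can be offered.

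A reader might infer that the protocol intends severe liver injury to be treated through, or that dose-reduced cases escape expert review. The documents do not support either: HERC sees every such elevation, and the wording points to stopping levels that were not written as such. The key endpoint of ALT >3x ULN is unaffected, since the elevation counts whatever is done about dose.

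The conclusion rests on the literal wording of the protocol and SAP. The HERC and IDMC charters are separate documents and were not available; a stopping rule there would narrow the gap, though sites work from the protocol. SAP Section 12 records early termination with 5 participants randomized. That limits actual exposure but does not alter the wording.

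**What to change.** - **In 7.3.7.1, add:** *If any of the three limits is met, study drug must be interrupted; dose reduction is not an alternative, and drug may be given again only under the HERC exception.*
- **In 7.3.7.1.2, add:** *Continuing or re-initiating titration, or Part 2 re-titration, is subject to the three limits and the HERC exception in 7.3.7.1.*
- **Keep** the choice of reduction or interruption, after consultation, for elevations >3x ULN that meet none of the limits.

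The direct cost is two sentences. The downside is a few more interruptions among participants at these levels, with what Section 4.2.3 already attaches to them: three creatinine and cystatin C samples if the break is expected to last 7 days or more, a post-baseline MRI if it is expected to exceed 4 weeks or be permanent, and permanent discontinuation of study drug if it exceeds 8 weeks.

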7.3.7.1.1 Repeat Liver Testing in Participants with Abnormal Values at Screening

Participants with aminotransferase or total bilirubin values above the values in the exclusion criteria ($>1.2 \times$ ULN) during Screening will not proceed further in the trial. However, if evaluation indicates a reversible cause of abnormal values, such participants may be re-screened when their liver chemistry tests return to values allowing entry into the trial.

